6.5.1 RESCUE MEDICINE

Not applicable.

7 STUDY INTERVENTION AND PARTICIPANT DISCONTINUATION/WITHDRAWAL

7.1 DISCONTINUATION OF STUDY INTERVENTION

Dose Delays and Dose Modifications:

Individual dose modification of daratumumab is not permitted, but dose delay is recommended as the primary method for managing daratumumab-related toxicities.

Daratumumab-Related Toxicity Management:

If any of the following criteria are met and the toxicity is more than expected daratumumab injection must be held to allow for recovery from toxicity. If attribution is unclear, then daratumumab should be held until recovery from toxicity as noted below.

The criteria for a dose delay are:

- Grade 4 hematologic toxicity
- Grade 3 thrombocytopenia with bleeding
- Febrile neutropenia
- Grade 3 or higher non-hematologic toxicities with the following exceptions:
 - Grade 3 nausea that responds to antiemetic treatment within 7 days
 - Grade 3 vomiting that responds to antiemetic treatment within 7 days
 - Grade 3 diarrhea that responds to antidiarrheal treatment within 7 days
 - Grade 3 fatigue that was present at baseline or that lasts for <7 days after the last administration of daratumumab

Grade 3 asthenia that was present at baseline or that lasts for <7 days after the last administration of daratumumab

Administration of daratumumab may be restarted upon recovery from toxicity to Grade 2 or baseline, with the exception that Grade 2 laryngeal edema or Grade 2 bronchospasm must be fully recovered. If daratumumab administration does not commence within the prespecified window of the scheduled administration date (Table 3), then the dose will be considered a missed dose. Administration may resume at the next planned dosing date.

Table 3: Daratumumab-related Toxicity Management

Daratumumab Dosing Frequency	Dose Missed	Dosing Resumption
Weekly	>3 days	Next planned weekly dosing date
Every 2 weeks	>7 days	Next planned every-2-weeks dosing date

Interruption or discontinuation from daratumumab SC infusions does not mean discontinuation from the study, and subjects will be asked to return for scheduled assessments as per the protocol at Visit 11, Visit 18, and Visit 19, if not already completed. If a clinically significant finding is identified (including, but not limited to changes from baseline) after enrollment, the investigator or qualified designee will determine if any change in participant management is needed. Any new clinically relevant finding will be reported as an adverse event (AE).

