2.3 RISK/BENEFIT ASSESSMENT

2.3.1 KNOWN POTENTIAL RISKS

While the package insert for the IV formulation of daratumumab (Darzalex) is provided for reference, it should be noted that it includes data for adverse effects in patients with multiple myeloma who were treated with various combination chemotherapy regimens. Furthermore, multiple myeloma is a hematological malignancy that can predispose patients to infection, anemia, thrombocytopenia, and leukopenia. As per the package insert, the safety data reflecting exposure to IV daratumumab 16 mg/kg monotherapy in 156 adult patients with relapsed and refractory multiple myeloma treated in three open-label, clinical trials, with median duration of exposure of 3.3 months (range: 0.03 to 20.04

months), are listed below. Serious adverse reactions were reported in 51 (33%) patients. The most frequent serious adverse reactions were pneumonia (6%), general physical health deterioration (3%), and pyrexia (3%). Adverse reactions resulted in treatment delay for 24 (15%) patients, most frequently for infections. Adverse reactions resulted in discontinuations for 6 (4%) patients. Adverse reactions occurring in at least 10% of patients are presented in Table 1. Table 2 describes Grade 3–4 laboratory abnormalities reported at a rate of $\geq 10\%$.

Table 1: Adverse reactions with incidence $\geq 10\%$ in patients with multiple myeloma treated with IV daratumumab 16 mg/kg

Adverse Reaction	DARZALEX 16 mg/kg N=156		
	Incidence (%)		
	Any Grade	Grade 3	Grade 4
Infusion reaction ^a	48	3	0
General disorders and administration site conditions			
Fatigue	39	2	0
Pyrexia	21	1	0
Chills	10	0	0
Respiratory, thoracic and mediastinal disorders			
Cough	21	0	0
Nasal congestion	17	0	0
Dyspnea	15	1	0
Musculoskeletal and connective tissue disorders			
Back pain	23	2	0
Arthralgia	17	0	0
Pain in extremity	15	1	0
Musculoskeletal chest pain	12	1	0
Infections and infestations			
Upper respiratory tract infection	20	1	0
Nasopharyngitis	15	0	0
Pneumonia ^b	11	6	0
Gastrointestinal disorders			
Nausea	27	0	0
Diarrhea	16	1	0
Constipation	15	0	0
Vomiting	14	0	0
Metabolism and nutrition disorders			
Decreased appetite	15	1	0
Nervous system disorders			
Headache	12	1	0
Vascular disorders			
Hypertension	10	5	0

^a Infusion reaction includes terms determined by investigators to be related to infusion, see below.

^b Pneumonia also includes the terms streptococcal pneumonia and lobar pneumonia.

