2.3.3 ASSESSMENT OF POTENTIAL RISKS AND BENEFITS

As there are no currently available disease-modifying treatments for AD, there is an adequate rationale to explore the potential efficacy of daratumumab in this small open-label study. The safety profile of daratumumab has been well-characterized in patients with multiple myeloma. Since the AD subjects to be enrolled in this study will be otherwise healthy, without history or evidence of malignancy, cardiac, pulmonary, or other significant medical illnesses or laboratory abnormalities, we expect the risk of adverse hematological effects or infectious complications to be lower than in patients with multiple myeloma. In view of the potential for daratumumab to interfere with the Indirect Antiglobulin Test (indirect Coombs test), and mask detection of antibodies to minor antigens in the subject's serum, type and screen will be sent prior to treatment initiation. To minimize the risk of post-infusion reactions, individuals with a history of asthma or chronic obstructive pulmonary disease will be excluded, and subjects will be premedicated with montelukast 10 mg orally 1 to 3 hours prior to the first dose of daratumumab, diphenhydramine 25 mg orally 1 to 3 hours prior to each dose, acetaminophen 1000 mg orally 1 to 3 hours prior to each dose, and dexamethasone 20 mg orally 1 to 3 hours prior to the first 3 doses, 10 mg orally 1 to 3 hours prior to all subsequent doses, and 4 mg orally the day after each dose. To avoid hepatitis B virus reactivation, subjects with serologic evidence of current or prior hepatitis B infection will be excluded. To prevent herpes zoster reactivation, patients will also be treated with oral acyclovir 400 mg daily beginning the day after the first dose and continuing until 12 weeks after the final dose. After the first dose, subjects will have a CBC performed within 48 hours prior to each subsequent infusion, and the scheduled infusion will be held if there is evidence of clinically significant anemia, neutropenia, leukopenia, or thrombocytopenia. Additional safety laboratory monitoring will include a comprehensive metabolic panel (CMP) every 4 weeks.

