8.3.3.3 EXPECTEDNESS

The investigator will be responsible for determining whether an adverse event (AE) is expected or unexpected. An AE will be considered unexpected if the nature, severity, or frequency of the event is not consistent with the risk information previously described for the study intervention.

An adverse event is considered unlisted if the nature or severity is not consistent with the applicable product reference safety information. For a medicinal product(s) with a marketing authorization, the expectedness of an adverse event will be determined by whether or not it is listed in the applicable product information.

<http://www.darzalex.com/shared/product/darzalex/darzalex-prescribing-information.pdf>

For daratumumab, the expectedness of an adverse event will be determined by whether or not it is listed in the Investigator's Brochure.

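### Section 7.1 makes the mandatory dose hold depend on an undefined expectedness condition, so on one reading a known, clearly related Grade 3 infection need not be held

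*Combined protocol and SAP*

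**What the plan says.** Section 7.1 permits no dose reduction and states that "dose delay is recommended as the primary method for managing daratumumab-related toxicities". The mandatory rule follows: "If any of the following criteria are met and the toxicity is more than expected daratumumab injection must be held". The next sentence deals with doubtful causality: "If attribution is unclear, then daratumumab should be held until recovery from toxicity as noted below".

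The list that follows covers Grade 4 hematologic toxicity, Grade 3 thrombocytopenia with bleeding, febrile neutropenia, and non-hematologic toxicity of Grade 3 or higher. The exceptions are certain cases of Grade 3 nausea, vomiting, diarrhea, fatigue and asthenia. Infection is not among them. The line introducing the list calls these the dose-delay criteria and attaches no expectedness condition. Restart, at Grade 2 or baseline, carries none either.

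Two other sections bear on what is expected. Section 8.3.3.3, on classifying adverse events, says: "An AE will be considered unexpected if the nature, severity, or frequency of the event is not consistent with the risk information previously described". It adds: "For daratumumab, the expectedness of an adverse event will be determined by whether or not it is listed" in the Investigator's Brochure. Section 2.3.3 says of the trial population: "we expect the risk of adverse hematological effects or infectious complications to be lower than in patients with multiple myeloma".

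Section 2.3.3 also has its own laboratory rule, applied to the CBC taken before each dose after the first: "the scheduled infusion will be held if there is evidence of clinically significant anemia, neutropenia, leukopenia, or thrombocytopenia".

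**The concern.** The mandatory sentence needs two things at once: a listed criterion and toxicity beyond what is expected. If expected means known for the drug, the condition exempts the events most likely to call for a hold. Section 2.3.1 names pneumonia as the most frequent serious adverse reaction. It also reports that adverse reactions delayed treatment in 24 of 156 patients (15%), most often because of infection.

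The order of protection is then inverted. A severe infection of uncertain cause gets a specific instruction to hold, while one clearly caused by the drug may get only a general recommendation to delay.

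At stake is whether two careful physicians would act alike before the next dose, which is due within a week during the weekly phase. Each further dose also brings dexamethasone, 10 or 20 mg beforehand and 4 mg the day after (6.1.3).

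**Working it through.** **Step 1: two readings of the condition.**

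- Reading A takes expected from the Brochure-listing rule in 8.3.3.3. The Brochure is not among the documents. That it lists pneumonia is an assumption, supported by Table 1 in 2.3.1 (pneumonia 11% any grade, 6% Grade 3, N=156).
- Reading B uses the severity and frequency wording in 8.3.3.3 together with the lower risk expected in 2.3.3. A severe infection in this population then exceeds expectation.

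| Event | Listed in 7.1? | Reading A | Reading B | Other hold rule |
|---|---|---|---|---|
| Grade 3 pneumonia, clearly related | Yes | Not mandatory | Must hold | None specific |
| Grade 3 pneumonia, attribution unclear | Yes | Should hold | Must hold | None specific |
| Isolated Grade 4 lymphopenia, related | Yes | Not mandatory | Must hold | 2.3.3 names leukopenia, not lymphopenia |
| Grade 4 neutropenia or thrombocytopenia, related | Yes | Not mandatory under 7.1 | Must hold | 2.3.3, if clinically significant |
| Grade 3 anemia | No | No 7.1 criterion | No 7.1 criterion | 2.3.3, if clinically significant |
| Grade 3 injection-related reaction | Has its own rule | Stop (6.1.5) | Stop (6.1.5) | 6.1.5, no expectedness test |

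The readings lead to different actions in rows 1 and 3. In row 2 they differ only in strength. In row 4 the CBC hold in 2.3.3 closes most of the gap.

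Reading A also sits badly with 7.1 itself. Table 2 lists Grade 4 lymphopenia (10%), thrombocytopenia (8%) and neutropenia (3%). If known means expected, the first listed criterion is largely emptied. That suggests a drafting fault, not an intended exemption.

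**Step 2: how often the rule could be called on.** The plan gives no figure to reproduce. With n = 15 subjects and rate p, the expected number is 15p and the chance of at least one case is 1 − (1 − p)^15. The two lower rates are assumptions, because 2.3.3 expects lower risk but gives no number.

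| Grade 3 pneumonia rate | Expected cases | Chance of at least one |
|---|---|---|
| 6% (IV myeloma data) | 15 × 0.06 = 0.90 | 1 − 0.94^15 = 60% |
| 3% (half, assumed) | 15 × 0.03 = 0.45 | 1 − 0.97^15 = 37% |
| 1.2% (one fifth, assumed) | 15 × 0.012 = 0.18 | 1 − 0.988^15 = 17% |

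Grade 3 hypertension is not counted. The subcutaneous data in 2.3.1 place its Grade 3 events among injection-related reactions, which 6.1.5 covers.

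**Step 3: doses affected if the condition is removed.**

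- Planned doses: 8 weekly + 8 every two weeks = 16 per subject, and 16 × 15 = 240 in all.
- Grade 4 lymphopenia cases: 15 × 0.10 = 1.5 at the Table 2 rate, 0.75 at half and 0.3 at one fifth (the last two assumed).
- If each case misses 1 to 4 doses (assumed), the total at the Table 2 rate is 1.5 to 6 of 240, or 0.6% to 2.5%. At one fifth it is 0.3 to 1.2 of 240, or 0.1% to 0.5%.
- An affected subject would lose 1/16 = 6% to 4/16 = 25% of planned doses.

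**The case against.** The strongest reply is that 7.1 already answers the question. Its list is introduced, without condition, as the criteria for delaying a dose. Grade 3 infection falls within it, and the restart threshold applies to any held event. Reading A borrows a classification rule that 7.1 does not cite and treats a comparative phrase as though it meant unlisted. It relies on a Brochure that cannot be seen here, and it undoes the list it introduces.

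Other safeguards exist. Vital signs, including temperature and respiratory rate, are taken before every infusion (8.2), and adverse events are reviewed at Visits 1 to 19. The end of 7.1 has the investigator decide on management after any clinically significant finding, and 7.2 allows withdrawal for any adverse event. The Independent Safety Monitor is told of serious events within 24 hours (10.1.6).

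Much of this stands. Reading A is the weaker reading, and the safeguards make it unlikely that a physician would knowingly inject a subject with active severe pneumonia. But they leave the decision to judgment or provide oversight; none is a hold rule for infection. The unconditional list heading also does not remove the condition from the one sentence that says must.

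A reader might infer that the protocol permits dosing through severe infection, or that 7.1 and 2.3.3 contradict each other on cytopenias. The documents support neither. Delay is recommended for all daratumumab-related toxicity. The two cytopenia triggers differ in threshold, but staff satisfy both by holding when either applies.

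**Conclusion.** The point holds as a gap in the mandatory rule only. For a known, clearly related Grade 3 non-hematologic event that is neither an injection reaction nor a listed exception, and possibly for isolated Grade 4 lymphopenia, the text can be read as requiring a hold or as merely recommending delay. Infection is the main case. The cytopenia mismatch is minor, because the hold in 2.3.3 covers clinically significant anemia, neutropenia, leukopenia and thrombocytopenia without an expectedness test.

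The 17% to 60% range rests on carrying an intravenous myeloma rate, or assumed fractions of it, over to 15 subjects with Alzheimer's disease. It should not be read as the chance of a missed hold, which the documents give no basis for estimating. Confidence is medium: the missing definition is plain on the page, while its practical effect depends on how physicians read the sentence. This is a cheap improvement to a safety rule, not evidence that the trial is unsafe.

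**What to change.** In 7.1, delete the expectedness condition so that meeting any listed criterion requires a hold until recovery. Keep the listed Grade 3 exceptions and the unclear-attribution sentence.

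Optionally add: *The pre-dose CBC hold in Section 2.3.3 applies in addition; a dose held under it resumes when the investigator judges the cytopenia no longer clinically significant.* The separate resumption condition is needed because a Grade 2 cytopenia held under 2.3.3 would already meet 7.1's restart threshold.

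The edit is one clause removed and, at most, one sentence added. The real cost is a few more held or missed doses, chiefly for Grade 4 lymphopenia: roughly 0.1% to 2.5% of planned doses across the assumptions in the working. An affected subject could lose noticeable exposure before the week-25 endpoint, and more than shown if recovery is slow. Doses that would be held under the present text anyway are not an added cost.

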7.2 PARTICIPANT DISCONTINUATION/WITHDRAWAL FROM THE STUDY

Participants are free to withdraw from participation in the study at any time upon request. An investigator may discontinue or withdraw a participant from the study for the following reasons:

1. Significant study intervention non-compliance
2. If any clinical adverse event (AE), laboratory abnormality, or other medical condition or situation occurs such that continued participation in the study would not be in the best interest of the participant
3. If the participant meets an exclusion criterion (either newly developed or not previously recognized) that precludes further study participation

The reason for participant discontinuation or withdrawal from the study will be recorded on the Case Report Form (CRF).

7.3 LOST TO FOLLOW-UP

A participant will be considered lost to follow-up if he or she fails to return for 2 scheduled visits and is unable to be contacted by the study site staff.

The following actions must be taken if a participant fails to return to the clinic for a required study visit:

1. The site will attempt to contact the participant and reschedule the missed visit if feasible and counsel the participant on the importance of maintaining the assigned visit schedule and ascertain if the participant wishes to and/or should continue in the study.
2. Before a participant is deemed lost to follow-up, the investigator or designee will make every effort to regain contact with the participant (where possible, 3 telephone calls and, if necessary, a certified letter to the participant's last known mailing address or local equivalent methods). These contact attempts should be documented in the participant's medical record or study file.
3. Should the participant continue to be unreachable, he or she will be considered to have withdrawn from the study with a primary reason of lost to follow-up.

8 STUDY ASSESSMENTS AND PROCEDURES

8.1 EFFICACY ASSESSMENTS

Alzheimer's Disease Assessment Scale-cognitive subscale (ADAS-Cog): The ADAS-Cog is the most widely used cognitive scale in AD clinical studies. The standard 11-item version (ADAS-Cog/11) includes both subject-completed tests and observer-based assessments. Specific tasks include Word Recall, Naming Objects and Fingers, Commands, Constructional Praxis, Ideational Praxis, Orientation, Word Recognition, and Language. The score ranges from 0 to 70 with each point representing a performance error and higher scores reflecting worse performance (Rosen et al. 1984). An improvement (decrease) of ≥ 4 points in ADAS-cog/11 score has been deemed to be clinically meaningful (Raina et al. 2008). The 12-item version (ADAS-Cog/12) adds a delayed word recall task, scored from 0 to 10. The ADAS-Cog/12 score is the total of the ADAS-Cog/11 plus the delayed recall score, and therefore has a range of 0 to 80 (Sano et al. 2011). The ADAS-Cog will be administered at the Screening Visit, Visit 11, Day 85+/-2, Visit 18, Day 176+/-3, and Visit 19, Day 246+/-7.

Clinical Dementia Rating Scale Sum of Boxes (CDR-SB): The CDR is a clinical global rating scale requiring the interviewing of both the subject and a study partner who knows and has contact with the subject. The CDR is a clinician-directed assessment of both cognition and function, and is intended to capture the state and therefore the disease stage of the individual (Hughes et al. 1982). The CDR-SB has been proposed as an acceptable approach for following disease progression and confirming treatment in AD (Lynch et al. 2006). The CDR assesses 6 domains of subject function: memory, orientation, judgment and problem solving, community affairs, home and hobbies and personal care. Each of these items has a maximum possible score of 3 points and the total score is a sum of the item scores (sum of boxes) giving a total possible score of 0 to 18, with higher scores indicating more impairment. The CDR will be administered at the Screening Visit, Visit 11, Day 85+/-2, Visit 18, Day 176+/-3, and Visit 19, Day 246+/-7.

Mini Mental State Examination (MMSE): The MMSE is a 30-point scale that measures orientation to time and place, registration, immediate and delayed recall, attention, language, and drawing (Folstein et al. 1975). Scores range from 0 (most impaired) to 30 (no impairment). The MMSE will be administered at the Screening Visit, Visit 11, Day 85+/-2, Visit 18, Day 176+/-3, and Visit 19, Day 246+/-7.

AD Composite Score (ADCOMS): The ADCOMS is a composite score derived from a weighted combination of selected items from the ADAS-cog/12, MMSE, and CDR-SB. The range of the ADCOMS is between 0 and 1.97. A higher score is indicative of greater impairment. Items contributing to the ADCOMS include 4 items of the ADAS-cog, two items of the MMSE (scored in reverse, as item maximum score minus measured score), and all six items of the CDR-SB (Wang et al. 2016).

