1.2 SCHEMA

1.3 SCHEDULE OF ACTIVITIES (SOA)

	Screening Dav.-60 to -1	Baseline Visit 1, Dav.1	Study Visit 2 Dav.8 +/-1 dav	Study Visit 3 Dav.15 +/-1 dav	Study Visit 4 Dav.22 +/-1 dav	Study Visit 5 Dav.29 +/-1 dav	Study Visit 6 Dav.36 +/-1 dav	Study Visit 7 Dav.43 +/-1 dav	Study Visit 8 Dav.50 +/-1 dav	Study Visit 9 Dav.64 +/-2 days	Study Visit 10 Dav.78 +/-2 days	Study Visit 11 Dav.85 +/-2 days	Study Visit 12 Dav.92 +/-2 days	Study Visit 13 Dav.106 +/-2 days	Study Visit 14 Dav.120 +/-2 days	Study Visit 15 Dav.134 +/-2 days	Study Visit 16 Dav.148 +/-2 days	Study Visit 17 Dav.162 +/-2 days	Study Visit 18 Dav.176 +/-3 days	Final Study Visit 19 Dav.246 +/-7 days
Procedures																				
Informed consent	X																			
Demographics	X																			
Medical history	X																			
Administer daratumumab SC		X	X	X	X	X	X	X	X	X	X		X	X	X	X	X	X		
Physical and neuro exam	X											X							X	X
Vital signs	X	X	X	X	X	X	X	X	X	X	X	X	X	X	X	X	X	X	X	X
Height	X																			
Weight	X	X	X	X	X	X	X	X	X	X	X		X	X	X	X	X	X	X	X
12-lead ECG	X																			
CBC	X		X	X	X	X	X	X	X	X	X		X	X	X	X	X	X		X
Comprehensive metabolic panel	X				X				X		X			X		X		X		X
PT/INR, APTT, TSH, B12 level	X																			
Hepatitis B surface antigen and core antibody	X																			
Hepatitis C Virus antibody	X																			
HIV antigen/antibody screen	X																			
Brain MRI	X																		X	
Amyloid PET scan of brain	X																			
Type and screen		X																		
Flow cytometry		X																	X	
Concomitant medications	X	X	X	X	X	X	X	X	X	X	X	X	X	X	X	X	X	X	X	X
Adverse events review		X	X	X	X	X	X	X	X	X	X	X	X	X	X	X	X	X	X	X
Modified Hachinski (MHIS)	X																			
GDS	X																			
CDR	X											X							X	X
MMSE	X											X							X	X
ADAS-Cog	X											X							X	X

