1. Side effects of dexamethasone may include nausea, vomiting, heartburn, headache, dizziness, trouble sleeping, appetite changes, increased sweating, high blood sugar, mood swings, bleeding from the stomach, swelling of the hands or feet, and bone damage.
2. The most common adverse reactions in adult patients treated with acetaminophen (Tylenol) are nausea, vomiting, headache, and insomnia.
3. Side effects of diphenhydramine (Benadryl) may include sleepiness, confusion, dizziness, incoordination, dry mouth, blurred vision, upset stomach, constipation, and difficulty urinating.
4. The most common adverse reactions to montelukast (incidence >5% and greater than placebo, listed in descending order of frequency) are upper respiratory infection, fever, headache, pharyngitis (sore throat), cough, abdominal pain, diarrhea, otitis media (ear infection), influenza, rhinorrhea (runny nose), and sinusitis (inflammation of sinuses).
5. Side effects of acyclovir may include nausea, vomiting, dizziness, diarrhea, sleepiness, and confusion.

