5 STUDY POPULATION

5.1 INCLUSION CRITERIA

In order to be eligible to participate in this study, an individual must meet all of the following criteria:

1. Each subject must be ≥ 55 to ≤ 85 years of age at the screening visit.
2. Each subject must have a diagnosis of probable AD dementia according to National Institute on Aging-Alzheimer's Association (NIA-AA) criteria.
3. Each subject must have a Mini-Mental State Examination (MMSE) score ≥ 15 and ≤ 26 at the screening visit.
4. Each subject must have a Magnetic Resonance Imaging (MRI) scan performed during the screening period that is consistent with a diagnosis of AD.
5. Each subject must have a positive amyloid Positron Emission Tomography (PET) scan, either performed during the screening period, or previously performed provided that the scan and result are considered acceptable by the investigator.
6. If the subject is receiving a cholinesterase inhibitor (donepezil, rivastigmine, or galantamine) and/or memantine, the dose must have been stable for at least 12 weeks before the screening visit, and the subject must be willing to remain on the same dose for the duration of the trial.
7. Each subject must have a study partner who is reliable and competent. The study partner must have a close relationship with the subject, have face to face contact at least 3 days/week for a minimum of 6 waking hours/week, and be willing to accompany the subject to all required study visits.
8. Each subject must have no clinically significant abnormal laboratory test results [complete blood count (CBC), prothrombin time (PT)/international normalized ratio (INR), activated partial thromboplastin time (APTT), comprehensive metabolic panel (CMP), thyroid stimulating hormone (TSH), and vitamin B12 level] at the screening visit.
9. Each subject must have results of a physical and neurological examination and vital signs within normal limits or clinically acceptable to the investigator at the screening visit.

10. If female, the subject must be postmenopausal defined as: No menses for 12 or more months without an alternative medical cause OR permanently surgically sterile (bilateral oophorectomy, bilateral salpingectomy, or hysterectomy).

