minimize the risk of injection site hematomas, anticoagulant medications, including warfarin, dabigatran, rivaroxaban, apixaban, edoxaban, heparin, or enoxaparin, are also prohibited throughout the treatment phase of the study (through Visit 17). Live/live-attenuated bacterial or viral vaccines are prohibited from 3 months prior to the screening visit and throughout the treatment phase of the study (through Visit 17). This includes oral typhoid, oral cholera, measles, mumps, rubella, oral polio (Sabin), yellow fever, varicella (Varivax or Zostavax), rotavirus, Japanese encephalitis, or live-attenuated influenza (FluMist) vaccines. Treatment with immunosuppressive medications, such as azathioprine, cyclosporine, methotrexate, tacrolimus, or mycophenylate, is prohibited from 2 months prior to the screening visit and throughout the treatment phase of the study (through Visit 17). Treatment with courses of corticosteroids longer than 5 days are prohibited from 2 months prior to the screening visit and throughout the treatment phase of the study (through Visit 17). Due to potential interactions with rHuPH20 that could slow absorption of study medication, treatment with estrogens, or aspirin at a dose higher than 325 mg daily, is prohibited throughout the treatment phase of the study (through Visit 17). Medications that could have adverse effects on cognition, including opioid analgesics, centrally acting anticholinergic medications, sedative/hypnotic medications, and benzodiazepines, are not to be used within 72 hours prior to cognitive testing (at Screening, Visit 11, Visit 18, and Visit 19).

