Blood tests: Blood tests to be collected at the Screening Visit will include complete blood count (CBC), comprehensive metabolic panel (CMP), prothrombin time (PT)/international normalized ratio (INR), activated partial thromboplastin time (APTT), thyroid-stimulating hormone (TSH), vitamin B12 level, hepatitis B surface antigen (HBsAg), hepatitis B core antibody (HBcAb), hepatitis C virus antibody (HCVAb), and human immunodeficiency virus antigen/antibody screen (HIVAg/Ab). Blood samples will be obtained at Visit 1, prior to the first infusion, for type and screen and flow cytometry. After the first dose, subjects will have a CBC performed within 48 hours prior to each subsequent infusion (Visits 2 through 10 and 12 through 17). Additional safety laboratory monitoring will include a CMP every 4

weeks (Visits 4, 8, 10, 13, 15, and 17). CBC and CMP will also be obtained 12 weeks after the final dose (Visit 19).

Brain MRI: Brain MRI will be performed within the screening period and at Visit 18. MRI acquisition will be performed on a 3T MRI scanner (Siemens MAGNETOM Prisma). The sequences obtained will include proton magnetic resonance spectroscopy (¹H-MRS) from a mid-sagittal oblique 10.8 cm³ (2 × 2 × 2.7 cm) voxel in the region of the precuneus and posterior cingulate cortex.

Amyloid PET scan of brain: An amyloid PET scan may be performed within the screening period to confirm deposition of amyloid in the brain. A historical amyloid positive PET scan may be used provided that the scan and result are considered acceptable by the investigator.

Concomitant medications: Concomitant medications will be recorded at the Screening Visit and reviewed and updated at Visits 1-19.

Adverse events review: Subjects and study partners will be asked about adverse events at Visits 1-19. Adverse events will also be assessed if they are reported at any other time during the study by the subject or study partner, in person or by telephone.

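### The only pre-treatment ADAS-Cog is at Screening (Day -60 to -1), so the 25-week primary change can span 24.7 to 34.0 weeks and include up to 60 untreated days

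*Combined protocol and SAP*

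**What the plan says.** Section 8.1 fixes the test dates for the primary measure: "The ADAS-Cog will be administered at the Screening Visit, Visit 11, Day 85+/-2, Visit 18, Day 176+/-3, and Visit 19, Day 246+/-7". It gives the same four visits for the CDR and the MMSE. The Schedule of Activities (Section 1.3) and the list of cognitive test visits in Section 6.5 agree with it.

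In the Schedule the two pre-treatment columns are headed "Screening Dav.-60 to -1" and "Baseline Visit 1, Dav.1" (in the machine-read text, Day appears as Dav.). The second column is the first dosing visit and has no cognitive test.

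Sections 9.1 and 9.4.9 describe baseline only as preceding the start of treatment. Section 9.4.2 defines a responder as a subject who improves by at least 4 ADAS-cog/11 points from baseline to 25 weeks, and analyses the crude proportion with an exact 95% interval. It expects 2 to 3 points of worsening over 6 months and a reference responder rate of 20%. Section 9.2 regards further study as warranted if 7 or more of 15 subjects respond.

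One exploratory measure is handled differently. Section 8.2 says: "Blood samples will be obtained at Visit 1, prior to the first infusion, for type and screen and flow cytometry".

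**The concern.** The plan holds the end of the primary interval to within 3 days but lets the start fall anywhere in a 60-day window. The measured change is the sum of untreated change before Day 1 and change on treatment, and the untreated part differs between subjects. Nothing caps the lead-in except the screening window, no analysis takes it into account, and there is no control arm to absorb it.

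On the plan's own expectation, untreated change is worsening, so it makes a 4-point improvement harder to reach. With a decision based on a count in 15 subjects, the likely harm is a missed signal. The cognitive secondary endpoints (ADAS-cog/12, MMSE, CDR-SB, ADCOMS) share the same baseline, and their criterion of no worsening has no margin for drift. The exploratory 12-week change is stretched in the same way.

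**Working it through.** **1. The plan's own figures.** From Day 1, Visit 18 on Day 176 is (176 - 1)/7 = 25.0 weeks, so 25 weeks is counted from first dose. All 16 rows of the exact-interval table in Section 9.2 reproduce, including the lower limit of 0.213 for 7 of 15.

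**2. The interval actually measured.** With no Day 0, the time from Day -s to Day d is d + s - 1 days.

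| Change | Shortest | Longest |
|---|---|---|
| Visit 18 from Day 1 | 172 d = 24.6 wk | 178 d = 25.4 wk |
| Visit 18 from Screening | Day -1 to 173: 173 d = 24.7 wk | Day -60 to 179: 238 d = 34.0 wk |
| Visit 11 from Screening | Day -1 to 83: 83 d = 11.9 wk | Day -60 to 87: 146 d = 20.9 wk |
| Visit 18, baseline in Day -14 to -1 | 173 d = 24.7 wk | Day -14 to 179: 192 d = 27.4 wk |

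The spread of the primary interval is 238 - 173 = 65 days, of which 59 come from the screening window and 6 from the Visit 18 window. With a 14-day cap it is 192 - 173 = 19 days. Counting a Day 0 moves the limits by about 0.1 week.

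**3. Untreated drift.** Drift = m × lag/182.5, with m = 2 to 3 points per 6 months (Section 9.4.2): 0.15-0.23 points at 14 days, 0.33-0.49 at 30 days, 0.66-0.99 at 60 days.

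**4. Spread of the change score.** The documents give no SD. Assuming normal change, the 20% rate and the drift imply Φ((-4 - m)/SD) = 0.20, so SD = (4 + m)/0.8416 = 7.13, 7.72 and 8.32 for m = 2, 2.5 and 3.

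**5. Effect on the decision rule.** Let p0 be the true responder rate with no lag. Then p(lag) = Φ((SD·Φ⁻¹(p0) - m·lag/182.5)/√V). V is SD² (fixed), SD²(0.5 + 0.5(175 + lag)/175) (half), or SD²(175 + lag)/175 (proportional). P(go) = P(X ≥ 7 | n = 15, p), with p averaged over the lags.

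Worked case: p0 = 7/15, m = 3, lag 60, fixed V. The numerator is 8.32 × (-0.0837) - 0.99 = -1.68, so p = Φ(-0.202) = 0.420 and P(go) = 0.453.

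P(go) at a true 7/15, shown as m = 2 / m = 3 (no lag: 0.599):

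| Lags | Fixed | Half | Proportional |
|---|---|---|---|
| Even over 1-60 days | 0.542 / 0.525 | 0.549 / 0.533 | 0.555 / 0.540 |
| 60 days for all | 0.485 / 0.453 | 0.502 / 0.472 | 0.515 / 0.487 |
| Even over 1-14 days | 0.585 / 0.581 | 0.587 / 0.583 | 0.588 / 0.584 |
| 14 days for all | 0.573 / 0.566 | 0.576 / 0.568 | 0.578 / 0.571 |

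Comparing the even-spread rows, the cap recovers 0.03-0.06. Expected responders lost, of 15, are 0.21-0.36 with the 60-day window and 0.06-0.09 with the 14-day window.

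At a true 0.55, P(go) is 0.82 with no lag, 0.76-0.78 with lags even over 60 days, and 0.80-0.81 with lags even over 14 days.

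**6. False go.** At a true 0.20, P(X ≥ 7) is 0.018. Across these scenarios it ranges from 0.007 (60 days for all, fixed V, m = 3) to 0.023 (60 days for all, proportional V, m = 2).

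**The case against.** The facts and arithmetic are not in dispute; the weight is. Baseline can be identified, because only one pre-treatment score exists. The effect on P(go) depends on a lag distribution that the documents do not give. If lags were even over Day -30 to -1, P(go) at a true 7/15 would be 0.56-0.58 and the cap would recover only 0.01-0.02. At a true 0.60 with lags even over 60 days, it would recover 0.02-0.03. The SD is back-solved and varies only with the drift, and practice effects are set to zero. Section 9.2 claims no formal power. The 20% reference may itself contain a lead-in, in which case a screening baseline would be like for like. Day -14 is not derived from the documents, and adjustment in 15 subjects is impractical.

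Most of this stands as a limit on size. It does not change the interval, which needs no model. No mismatch with the 20% rate is claimed, since that cannot be settled from the documents. The remedy is a change of schedule, not an adjustment, and 14 days is a practical choice.

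A further point is that exclusion 25 asks whether impairment or limited English would prevent collection of outcomes, which an ADAS-Cog at Screening could inform. That is an investigator's judgement. The Screening MMSE and interview can inform it, and the criterion does not call for an ADAS-Cog score.

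**Conclusion.** The concern holds. The primary 25-week change may span 24.7 to 34.0 weeks, with a subject-specific untreated lead-in of up to 60 days that is neither capped further nor adjusted for.

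The consequence is minor to moderate. With lags spread evenly over the window, P(go) at a true 7/15 falls by 0.04-0.07 (from 0.60 to 0.53-0.56); 0.45-0.52 is reached only if every subject has the full 60 days. The likely error is a missed signal, and the false-go chance stays between 0.007 and 0.023. The 7-of-15 rule and its interval table are unaffected.

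The interval range rests only on the visit windows and the no-Day-0 convention. The P(go) figures also assume normal change, linear drift, an SD of 7.1-8.3 and an assumed lag distribution; practice effects could offset part of the loss. This is a cheap improvement to the primary measurement and should be made.

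**What to change.** - **Sections 1.3 and 8.1:** require the baseline ADAS-Cog and CDR, with a repeat MMSE, together on one non-dosing day within Day -14 to -1. Use an existing trip where possible: the Screening Visit itself if it falls in that window, or an imaging trip. Otherwise test at Visit 1 before any premedication, since Section 2.3.1 warns: "Side effects of diphenhydramine (Benadryl) may include sleepiness, confusion, dizziness, incoordination".
- **MMSE:** keep the Screening MMSE for eligibility. The repeat gives ADCOMS a single baseline date, because that score mixes scales: "Items contributing to the ADCOMS include 4 items of the ADAS-cog, two items of the MMSE", plus all six CDR items. No repeat is needed if the Screening Visit is within the window.
- **Section 9.4:** name this assessment as baseline for all cognitive endpoints, and report each subject's baseline-to-Visit 18 interval with the primary result.
- **Section 6.5:** add the new test date to the listed cognitive visits, so that the existing 72-hour rule covers it.
- **Spectroscopy:** its baseline can stay in Screening, because eligibility requires a "scan performed during the screening period that is consistent with a diagnosis of AD". Report that interval too.
- **If the schedule is not changed:** state in Section 9.4 that the screening score is the baseline, and still report the intervals.

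The cost is an amendment to the Schedule and the wording. ADAS-Cog and CDR scores are not eligibility criteria, so those tests are re-timed, not added. One short MMSE is added for subjects screened before Day -14, with a small practice effect. Some subjects and partners face a scheduling constraint or one extra trip. The Visit 1 option avoids the trip but puts baseline testing on a dosing day, unlike the follow-up tests.
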